The use of a multicenter study comprising more than one center, which will be several kilometers apart, will limit the possible geographical and environmental impact on the results of our sample in relation to the target population. In addition, routine screening of all patients presenting with TNS and negative EEG, in the setting of cSDH, regardless of the time of admission, will also ensure a more representative sample of the population.

In order to limit the bias of voluntarism, we have implemented several measures. First, it is important to minimize the number of patients who might decline to participate in the study. For that, we have constructed our study so that participation in the study does not involve additional testing or traveling than is already indicated by the primary pathology. In addition, we will educate patients on the equal effectiveness of the treatments that will be offered in the study and the fact that these two treatments are currently approved for the treatment of their condition. This should be reassuring. In addition, the availability of a member of the research team for any questions or side effects will also be a positive reason to participate. Ultimately, the substituted consent clause will help maintain eligibility for a significant proportion of patients, given the prevalence of confusion and neurocognitive disorder in the population with cSDH.

Measures to avoid dropouts

Once the randomization, it will be necessary to minimize the dropouts in order to maintain the random effect of the randomization and therefore a representative sample of the population. To begin with, it will be important to be readily available. Patients will have our contact details and a telephone follow-up will be carried out when problems arise. If necessary, a clinic appointment can be set. When side effects, it will be discussed with the patient to lower the dose, in order to reduce the side effects, before stopping the antiepileptic permanently. Of course, the final decision will be up to the patient.

In addition, the medication will be started in increasing doses, in order to limit side effects.

Limiting clinical appointments to what patients would have had without participating in the study, namely neurology follow-up and neurosurgery follow-up, should also limit dropouts by limiting the involvement required by patients.

Variables and data collection

Initial data

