The existence of propagated cortical depolarizations will be assessed by electrocorticography (ECoG) for some operated patients (see below for the detailed procedure) as well as by a surface EEG and a near infrared spectroscopy monitor. These paraclinical examinations will help to rule out a diagnosis of epilepsy and will provide the physiological data necessary for the confirmation of cortical depolarizations.

Side effects will be assessed and graded using CTCAE terminology (Common Terminology Criteria for Adverse Events)³¹.

After a first negative pre-randomization EEG, 2 more EEGs will be performed at 24 hour intervals in order to increase the diagnostic sensitivity of ictal activity. If an EEG is positive, there will be no further EEG. These EEG results will help for further validation of the NESIS score.

Magnetic resonance imaging will be recommended in patients with 3 negative EEGs, in order to rule out another structural cause, such as transient ischemic events. This will remain at the discretion of the clinician, depending on clinical relevance and availability of the examination..

Process

Initial meeting

Patients will be seen during their initial hospitalization following the diagnosis of TNS and their first negative EEG. If SDH evacuating surgery is planned for a patient who has already been randomized, they will be offered the installation of an ECoG monitor during the same surgery. This step will be optional. Subsequently, the patients will be reviewed postoperatively and the intervention will be started if transient neurological symptoms persist.

The meeting will be conducted by a research nurse or a member of the research team. An explanation of the study, drugs, goals, and intended patient involvement will be discussed. At this point, patients will have the choice of whether or not to sign the consent form. They will be given time for reflection, if desired. If the patient is participating in the study, demographic data, clinical characteristics of the subdural hematoma and characteristics of transient neurological symptoms will be collected using a standardized questionnaire (Appendix 3). Thereafter, treatment (TPM or LEV) will be assigned by randomization and started during hospitalization with a planned increase up to

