If the patient wishes to stop the antiepileptic drug, a trial of smaller doses of the same treatment will be offered. Upon refusal, or failure despite a reduction in doses, TPM will be offered to the patient if he had LEV and vice versa. This change of group will only be possible after 2 months from the beginning of treatment. These data will not be included in the calculation of the primary outcome, but can still be analyzed as a secondary outcome to assess whether changing patients from one group to another allows them to fully resolve the TNS. Patients who fail both treatments, or who refuse to attempt the treatment in the other group will be excluded from the remainder of the study and treatment with another antiepileptic recognized in the treatment of focal seizures as well as an usual follow-up will be offered.

Participant calendar

Table 4 – Participant calendar

Recruitment (Day 1)	Randomizatio n (After recruitment)	Phone follow-up (Week 2)	Clinic follow-up (Month 2)	Clinic follow-up (Month 4)	Phone follow-up (Month 6)
Standardized questionnaires : Epidemiological	Start of treatment	Medical assessment with	Medical assessment with	Medical assessment with	Medical assessment with
data Clinical features	EEG daily x 2 MRI if needed	standardized questionnaire	standardized questionnaire	standardized questionnaire	standardized questionnaire

Collection method

Sources: Data will be collected initially with the help of the patient's medical record. Subsequently, the rest will be completed entirely by the patient or his family. The evaluations will be guided by standardized questionnaires.

For patients with ECoG, continuous waveforms will be recorded for the entire period the electrode will be implanted, either up to the recording of 5 TNS episodes or up to 72 hours of recording.

The data will be collected double blind. The person administering the questionnaire and the person analyzing the data will not know the patient's group. In addition, a study number will be assigned to all patients during randomization and this is going to identify the patients on the questionnaires. Thus, the data will be entered into the Excel software anonymously. Following the study, the data will be kept for a period of 25 years, in a file locked with a password that will be in the research nurse's locked filing cabinet.

Data analysis

Statistics

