Safety monitoring: Every month, from the time when 10 patients have been recruited, safety data (dropout, major side effects (requiring discontinuation of treatment) and persistence of neurological symptoms (yes or no)) will be compared in both groups. If a difference of more than 50% is identified for any of these data, the ethics committee will immediately **be** informed. A modification or discontinuation of the study will then be evaluated for reasons of safety, theoretical efficacy or futility.

Limitations of the study

Obviously, our study includes several sources of bias that we anticipate, however we will try to limit their impacts.

Selection bias

The patients who will be selected in our study may not represent the target population of our study. Indeed, a bias of voluntarism is inherent in the estimate of our study. Patients agreeing to participate in a study often do not have the same characteristics as those refusing, causing a gap between the study population and the target population. To limit the impact of this bias, we have designed our study so that it does not represent additional displacement or test for patients, in order to limit refusals to participate. In addition, the use of a non-probability sample can lead to a reference bias. Patients attending the coordinating center may differ from those attending another, for environmental, geographic or other reasons. To limit this bias, by using a multicenter study, we took several centers that are geographically distant, which will represent the general population more fairly. In addition, the recruitment being done in a similar way for the two groups and the matching according to the home hospitals will allow to balance these possible differences which could interfere during the recruitment.

Measurement bias

Some fluctuation in the measuring instrument (questionnaire) may occur. In fact, over time, the patient may find the questionnaire redundant and become bored, and therefore respond less well to it. To limit the impact of this factor, we have limited the number of follow-ups. In addition, in order to balance this fluctuation in the two groups, we will use the same questionnaires in both groups.

Compliance bias

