Because TPM causes more side effects than LEV, compliance in this group may be lower. To limit the impact of this bias, active monitoring will be carried out with patients in the event of significant side effects, in order to reduce the dose of their treatment. This will limit drop-outs, as well as encourage better compliance. Then, the antiepileptics will be introduced gradually, in order to limit the side effects which would lead to a decrease in compliance.

Desirability bias

Because patients will know with which antiepileptic drug they will be assigned to, they could involuntarily change their different responses during assessments. Indeed, they might be tempted to demonstrate that TPM, treatment intervention, is more effective than it actually is. The same goes for side effects, which might be exaggerated by a patient knowing to take TPM, which is known to cause more side effects. To limit this bias, with the agreement of the ethics committee, we will approach patients during consent in a non-nominal manner. Indeed, while explaining that the two treatments are as effective as each other in epilepsy, we will explain that we want to demonstrate whether there is superiority of one of the two drugs over the other. Our hypothesis considering TPM being more efficient would remain confidential especially as this remains hypothetical. In the same sense, upon consent, all possible side effects will be presented in the form of a list, not distinguishing which are found more with which antiepileptic. Thus, even knowing the antiepileptic medication prescribed, patients will not be able to influence their responses for or against a particular treatment, not knowing which characteristics belong to which treatment. The two groups will therefore have the same potential information regarding their antiepileptic drug.

Other limitations :

The effect of Leveracetam on cortical depolarizations remains conflicting, however, if present, it may lessen the impact of our results. In addition, the favorable natural course of cortical depolarizations could mask the significant difference between our two groups.

Time and personnel management

Initial and follow-up in-clinic assessments will be performed during regular hospital hours. Telephone assessments will be carried out during the day or evening by a member of the research team.

Ethics

Consent

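### The monthly safety comparison counts a side effect only if it requires discontinuation, so a severe one managed by dose reduction without later stopping stays outside the comparison and its trigger

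*Protocol*

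**What the plan says.** **Monitoring rule.** Under Oversight mechanism, the Safety monitoring paragraph starts "Every month, from the time when 10 patients have been recruited, safety data" are compared in the two groups. It names three items: dropout, "major side effects (requiring discontinuation of treatment", and persistence of neurological symptoms. The trigger reads "If a difference of more than 50% is identified for any of these data"; the ethics committee is then informed, and modifying or stopping the study is considered. The same section declines an independent committee and leaves monitoring to the project team.

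**Handling of side effects.**
- Measures to avoid dropouts: "it will be discussed with the patient to lower the dose, in order to reduce the side effects, before stopping the antiepileptic permanently".
- Follow-up, for a patient who wishes to stop: "a trial of smaller doses of the same treatment will be offered".
- Compliance bias: "active monitoring will be carried out with patients in the event of significant side effects, in order to reduce the dose of their treatment".
- Appendix 5 (participant notebook): patients with bothersome or severe symptoms should tell the team, and the dose may be adjusted or the drug discontinued.

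**Severity data.** Measuring instrument: "Side effects will be assessed and graded using CTCAE terminology". Table 3 lists CTCAE severity as a tolerance variable for both drugs, and the Appendix 4 follow-up form has a grade column. Under Statistics, the side-effect rate is compared between groups as a secondary outcome.

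**The concern.** The monitoring rule classifies a side effect by what happens to the drug, while the rest of the protocol tries to keep patients on the drug at a lower dose. The two do not fit together. The policy that prevents discontinuation also removes the event from the only toxicity item that is watched during the trial. The CTCAE grade, which would show the event whatever was done about it, plays no part in the rule.

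At stake is timeliness. The final comparison will show these events, but only after patients have been exposed, when it can no longer prompt a modification. This matters more because the project team monitors its own trial. Compliance bias also expects more side effects on topiramate, so an imbalance is foreseeable.

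**Working it through.** The protocol states no figure for this point, so there is none to reproduce. The check is mainly a matter of following an event through the rule.

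| Course of a severe side effect | Monthly item it enters |
|---|---|
| Drug stopped because the side effect requires it | Major side effect |
| Dose lowered, this fails, drug then stopped for that reason | Major side effect, at the later date |
| Patient leaves the study | Dropout |
| Dose lowered, event settles, patient stays on the drug | None of the toxicity or dropout items |

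The third monitored item, persistence of neurological symptoms, measures efficacy and does not capture the last row. Compliance bias says that dose reduction is meant to limit drop-outs, so the dropout item does not pick up these events either.

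**What this does to the counted difference.** The protocol gives no toxicity rates, so what follows is an assumption shown over a range. Let pT and pL be the true proportions with a severe side effect on topiramate and levetiracetam. Let s be the share managed by dose reduction without later stopping, taken as equal in both arms. Then:

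- Counted difference = (pT − pL)(1 − s).
- Chance of crossing the trigger at one look = the sum of Bin(i; n, pT(1 − s)) × Bin(j; n, pL(1 − s)) over all i, j with |i − j|/n > 0.5. This reads the 50% as percentage points.
- n = 5 per arm at the first look (10/2), and n = 28 per arm at full recruitment (56/2), assuming equal allocation.

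| pT v pL (assumed) | s | Counted difference (points) | Chance, n = 5 | Chance, n = 28 |
|---|---|---|---|---|
| 60% v 5% | 0 | 55 | 0.598 | 0.631 |
| | 0.25 | 41.25 | 0.357 | 0.147 |
| | 0.5 | 27.5 | 0.147 | 0.005 |
| 80% v 10% | 0 | 70 | 0.822 | 0.967 |
| | 0.25 | 52.5 | 0.558 | 0.535 |
| | 0.5 | 35 | 0.264 | 0.048 |
| 40% v 5% | 0 | 35 | 0.264 | 0.048 |
| | 0.25 | 26.25 | 0.140 | 0.004 |
| | 0.5 | 17.5 | 0.052 | <0.001 |

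Two limits follow from the same arithmetic.

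1. On the percentage-point reading, the omission changes the trigger materially only when the true rates are far apart. At 40% v 5% and 28 per arm the trigger would rarely fire even with every event counted (0.048).
2. The protocol does not say whether the 50% is absolute or relative. On a relative reading with equal s, the expected ratio does not change: 60/5 = 12, and at s = 0.5, 30/2.5 = 12. Only unequal shares would distort it, and the protocol does not fix their direction. Compliance bias suggests more dose reduction on topiramate; Risks of participating in the study suggests more stopping.

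**The case against.** The strongest reply is that the protocol itself expects topiramate toxicity to show up as stopping. Risks of participating in the study calls its mainly gastrointestinal side effects frequent and reversible, and says they mainly lead to stopping the drug. Those events are what the rule counts. Dose reduction is also not the only path: the Intervention section allows the drug to be reduced or stopped, and the final decision is the patient's. This stands. It limits how many events are likely to be missed, but it does not bring a severe event that settles on a lower dose into the comparison.

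Three stronger readings are tempting, and the text does not support them.

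- *That such toxicity is never counted.* It is graded, it is a tolerance variable, and it enters the final comparison of side-effect rates. The omission is from the monthly comparison and its trigger.
- *That a mild event counts as major whenever the patient chooses to stop.* The rule speaks of side effects that require discontinuation, which is narrower than side effects followed by it.
- *That the item merely repeats dropout.* Under Follow-up, a patient who stops can be offered the other drug after two months and remain in the study, so discontinuing and dropping out differ.

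It can also be said that a treatment-limiting criterion is a legitimate choice for two drugs that the protocol describes as approved for focal seizures. That is why the discontinuation count should stay. It is no reason to leave the grade unused.

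**Conclusion.** The point holds in a limited form. As written, the monthly comparison and the ethics-committee trigger leave out a severe side effect that is managed by dose reduction without later stopping, even though its grade is on file. This follows from the text alone and needs no assumed rate.

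Its practical size cannot be stated. It depends on the true severe side-effect rates, on the share settled by dose reduction and on how the 50% is read, and the protocol gives none of these. The table above shows what the omission could do under assumed rates; it is not an estimate of what it will do. A reader might infer that an excess of topiramate toxicity would go unnoticed, but the protocol does not support that, since it expects much of this toxicity to end in counted discontinuations. This is a cheap improvement to safety surveillance in a trial without an independent committee.

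**What to change.** In the Safety monitoring paragraph, keep the count of side effects requiring discontinuation and add one monitored item: the number of patients per arm with any side effect of CTCAE grade 3 or higher, whatever was then done with treatment, taken from the latest follow-up form. The existing trigger wording would cover the new item.

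The cost is one amended sentence and one more line in the monthly table, using grades that the Appendix 4 form already records. There are two downsides. Somewhat more events will reach the monthly review. Grades are updated only at the scheduled contacts (week 2, months 2, 4 and 6) or when a patient reports a problem, so some monthly tables will hold little new information.

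A separate count of dose reductions is not proposed. The form asks only whether the dose was changed, which does not separate reductions from planned increases. No dosing or clinical rule needs to change.

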Statistical analysis of the various data will be done with the help of the Statistical Package for the Social Sciences (SPSS) software. Most of the data will be analyzed by members of the research team. If necessary, the statistician of the CRC (Clinical Research Center) will be consulted.

The results will be analyzed by "intension-to-treat" given the expected dropouts in the two treatment groups.

Primary outcome: To assess the efficacy of TPM compared to LEV in the treatment of TNS in the context of SDH with negative EEG. To do this, it will be necessary to compare the rate of complete resolution of symptoms between the two groups. Our study comprising two independent groups and this variable being dichotomous (resolution: yes or no), a Chi-Square test will be used. This same test will also be used to compare the response of TPM in the NESIS versus non-NESIS subgroups and the same comparison with LEV will also

be performed. Subsequently, as sub-analyzes, the decrease in the frequency, intensity and duration of episodes (continuous variables) will also be compared in the two groups using a Student's T-test after validation of assumptions underlying the test.

Secondary outcome: tolerance to the antiepileptics used. To do this, we will analyze the comparison of the dropout rate (dichotomous variable: yes or no) and the side effect rate (categorical variable) using a chi-square test.

Degree of significance

We retained a significance level corresponding to an error α of 5%, whether a value p<0.05. The accepted beta error (β) is 10%, for a power of 90%.

Missing data

Patients with a large number of missing data or not including the data necessary to calculate the primary outcome will be excluded from the study. Those with some missing data that do not allow certain calculations of secondary outcomes will be kept in the study, however, the sample sizes of these analyzes will be clarified during writing.

Oversight mechanism

An independent results and dropout rate monitoring committee will not be necessary. However, monitoring will be carried out by the project team.

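### The monthly safety trigger includes persistence of symptoms, the complement of the primary endpoint, at a threshold below the planned effect, and opens an efficacy or futility review with no boundary

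*Protocol*

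**What the plan says.** The Oversight mechanism section sets a monitoring rule that runs "Every month, from the time when 10 patients have been recruited". Three items count as safety data: dropout, major side effects, and persistence of symptoms: "persistence of neurological symptoms (yes or no)) will be compared in both groups". The trigger is common to all three: "If a difference of more than 50% is identified for any of these data", the ethics committee is told at once, and a modification or discontinuation "will then be evaluated for reasons of safety, theoretical efficacy or futility". No other number is attached to that review.

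The same section states "An independent results and dropout rate monitoring committee will not be necessary" and that "monitoring will be carried out by the project team".

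The Statistics section defines the primary analysis as a chi-square test to "compare the rate of complete resolution of symptoms between the two groups", resolution being yes or no. The follow-up form (Appendix 4) records this as persistence yes/no, so the monitored item is one minus the primary endpoint.

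The Sample size section plans on 14% resolution with usual antiepileptics and 100% with the treatments aimed at cortical depression, both in NESIS patients.

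**The concern.** A safety trigger should fire when something unexpected goes wrong. Here one of its three items is the efficacy result, and the effect the trial is sized for is larger than the gap that raises the alarm. A trial going exactly to plan would therefore be expected to set off a review of discontinuation, possibly on about five patients per arm.

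The review names efficacy and futility as grounds, yet no efficacy or futility boundary stands behind it. At five per arm the alarm can fire on evidence far too weak for an efficacy decision. Futility in the sense of no effect cannot be read from a rule that reacts only to a large difference. At stake is an ad hoc decision about continuing the trial, prompted by the primary endpoint and made without a pre-set criterion.

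**Working it through.** **Inputs.** From Sample size: resolution 14% (LEV) and 100% (TPM) in NESIS, z-values 1.960 and 1.282, 15 NESIS patients per arm, a NESIS share of 72%, and 42 NESIS patients of 56 (75%). The 72% agrees with 13 NESIS patients (Introduction) among 18 with negative EEG (Sample disponibility), but that derivation is an inference. From Timeline: 24 months of randomisation. Assumptions: 1:1 allocation, blocks of four, threshold read as percentage points.

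**1. The plan's own figure.** 2N = 4(1.960 + 1.282)² × 0.57 × 0.43 / (0.14 − 1)² = 13.93, so N = 6.97, rounded to 7 per arm. This reproduces.

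**2. Planning effect against threshold.** In NESIS, persistence is 0.86 on LEV and 0 on TPM: 86 points against 50. Over all patients, if non-NESIS patients resolve equally on both drugs (assumption; the protocol gives no non-NESIS rate on TPM), the gap is share × 0.86:
- 0.72 × 0.86 = 0.619
- 0.75 × 0.86 = 0.645
- 0.59 × 0.86 = 0.507 (0.59 being 13 of the 22 in the Introduction)

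All three exceed 0.50, the last only just.

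**3. One look at five per arm.** A gap above 0.5 means at least three patients of five. With non-NESIS persistence set to 0, TPM has none persisting and the alarm probability is P(X ≥ 3), X ~ Bin(5, p), that is 10p³(1−p)² + 5p⁴(1−p) + p⁵.
- p = 0.619: 0.344 + 0.280 + 0.091 = 0.715
- p = 0.645: 0.757
- NESIS patients only, p = 0.86: 0.978

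**4. Strength of the weakest alarms.** 4/5 against 1/5: Fisher two-sided p = 0.206. 3/5 against 0/5: p = 0.167. With equal arms and persistence of 20-50% (assumption), one look at five per arm alarms with probability 4-11%.

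**5. Monthly looks and smaller effects.** The single-look column is exact binomial. The last column is simulated: 56 patients uniform over 24 months, looks from the 10th recruited, outcome known at once / after two months. NESIS share 72%, LEV persistence 0.619. The 73% row is the effect that 15 per arm detects with 90% power by the plan's formula: solving 2(3.242)² p̄(1−p̄)/(pe − 0.14)² = 15 gives pe = 0.727. The other TPM rates below 100% are assumptions.

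| TPM resolution in NESIS | Overall gap (points) | Alarm at 5+5 | Alarm at some look |
|---|---|---|---|
| 100% (plan) | 62 | 72% | 96% / 96% |
| 80% | 48 | 48% | 72% / 78% |
| 100%, half of non-NESIS persist on TPM | 48 | 49% | 75% / 76% |
| 73% | 42 | 41% | 64% / 70% |
| 60% | 33 | 30% | 42% / 53% |
| 50% | 26 | 23% | 30% / 43% |
| 40% | 19 | 17% | 21% / 35% |

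At a 75% share the planning effect gives 76% at 5+5 and 98% at some look.

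**6. What a usable boundary would do.** One look at 10 assessed NESIS patients per arm, Fisher two-sided p < 0.001: stopping probability at most about 0.0002 if the arms are equal, 0.845 at 14% against 100%, 0.217 at 14% against 80%.

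**The case against.** The strongest reply is that the rule only notifies. Telling an ethics committee of a gap above 50% in persisting symptoms is a defensible safeguard, and efficacy is a named ground, so firing under the planned effect may be intended. The point about notification stands. A reader might infer that the alarm stops the trial, or that it lifts the type I error (to about 13-16% from about 5% if each alarm counted as an efficacy finding and the final test kept p < 0.05). The text supports neither, because an alarm opens an evaluation and does not decide it.

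A reader might also infer that an alarm is more likely than not whatever the true effect. That fails at smaller gaps: at 33 points it is 42% without lag and 53% with a two-month lag, and it is lower below that.

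The high figures also depend on how patients are counted. The Follow-up section offers the other drug after two months. If the table used current status and every persisting LEV patient switched and resolved by month 3 (an extreme assumption), 96% would fall to about 30%. Timing matters too: that section puts maximum TPM effect at 17 weeks and the last contact at month 6, so week-2 persistence during titration is not yet the final endpoint, and the 5+5 figures need all ten recruits assessed.

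Two further readings fail. Collection method says "The person administering the questionnaire and the person analyzing the data will not know" the patient's group, while the project team compares arms monthly; comparison by coded arm could satisfy both, so this is no contradiction. Nor does persistence obscure the dropout and side-effect signals, since each item is compared separately.

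What survives is that the protocol itself fixes the item, schedule, threshold and grounds, and they do not fit its own planning effect. This is not a detail left to an analysis plan.

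**Conclusion.** The concern holds in a limited form and should be corrected. Persistence as a trigger item puts the primary endpoint under a monthly rule whose threshold, 50, lies below the planned 86 points in NESIS and about 62-65 points overall.

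If the planning effect is real, the alarm fires in 72-76% of trials at five per arm and in about 96-98% at some look. This assumes outcomes known at the look, counting on the randomised drug before any switch, percentage points, and equal non-NESIS resolution on both drugs. At overall gaps of 42-48 points it fires at some look in about 64-78% of trials, and at 19-33 points in about 21-53% (72% share).

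An alarm at five per arm can rest on Fisher p = 0.17-0.21, which is no basis for an efficacy decision, and it says nothing about futility in the sense of no effect. The consequence is a review without a criterion, not a demonstrated loss of error control.

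**What to change.** 1. Remove persistence from the 50% trigger and delete efficacy and futility as grounds on it. Do not substitute a routine by-arm persistence table, which would expose more interim efficacy data than the present rule. If the sponsor wants an early efficacy look, write one pre-set boundary on the primary endpoint at a named visit, for example the one in step 6 of the working.

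2. Keep the dropout and major side-effect triggers from 10 recruited patients. Put all randomised patients in the denominator, so that losses before the week-2 contact count, and state whether 50% means percentage points or a relative difference. The scale matters: if major side effects were 10% against 50% (assumption), a look at five per arm would alarm with probability 36% in points and 75% if relative to the larger rate.

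The cost is protocol wording. The downside is that there is no early efficacy stop unless a boundary is written. The example boundary is also strict: it would stop only 22% of trials at 14% against 80%.
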